## **Study Endpoints**

### **Study Endpoints**

The primary endpoint of the study will be to assess the rate of successful initial placement of a peripheral venous catheter in patients representing difficult venous access dependent on the method used. Secondary endpoints include various measures of efficacy and quality of peripheral venous catheter placement as a factor of the method used. The results will allow for estimation of the promise of NIR vein imaging for a future clinical use.

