## **Study Objectives**

The objective of this project is to define the effectiveness and therefore the role of NIR vein finders in adult patients with difficult peripheral venous access. The specific objective of the proposed randomized controlled trial is to test the clinical success rate of placing peripheral venous catheters in 'difficult' access patients using traditional peripheral venous catheter placement compared to two established methods utilizing NIR vein imaging. We hypothesize that the capability to successfully place lasting peripheral venous catheters is increased with the adjunct of the imaging technology, reducing the number of failed needle sticks, reducing the number of peripheral venous catheters placed throughout a patient's hospital stay, and reducing the need for more invasive catheters such as PICC lines. To test this hypothesis, we utilize a commercially available FDA-approved NIR vein finder which currently is already in clinical use at Lahey Hospital & Medical Center. We are planning to conduct a randomized controlled trial recruiting patients who as part of their routine clinical care will require placement of a peripheral venous catheter and who are considered to have a difficult peripheral venous access. Potential study patients will be randomized into 3 groups:

- Placement of peripheral venous catheter using conventional methods
- Use of a VeinViewer to visualize the most suitable target. Once the target has been identified and marked, the device will be placed aside and the peripheral venous catheter will be placed using conventional methods
- Identification of the most suitable target and placement of a peripheral venous catheter under constant imaging with a VeinViewer

To achieve the goals of this project, we have assembled a highly interdisciplinary team with expertise in clinical peripheral venous catheter placement, biomedical device development, and biostatistics to pursue the following specific aims:

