### **Secondary Objectives**

- to compare variables representing the ease of peripheral venous catheter placement, complication rates, and durability of the catheter within each study treatment arm

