### Peripheral Venous Cannulation and Randomization of Study Groups

Patients, who meet eligibility criteria and agree to participate in the study after an informed consent process, will undergo simple randomization. A sealed envelope holding the information of the random assignment will be opened by the Vascular Access Team member. Randomization will assign study patients into 1 of 3 groups/treatment arms with a 1:1:1 ratio:

- Placement of a peripheral venous catheter using conventional methods
- Use of VeinViewer to visualize the most suitable target. Once the target has been identified and marked, the device will be placed aside and the peripheral venous catheter will be placed using conventional methods
- Identification of the most suitable target and placement of a peripheral venous catheter under constant imaging with VeinViewer

When the VeinViewer device will be utilized, multiple areas on the patient's upper extremities will be assessed looking for the most suitable access point according to routine clinical practice. There is no restriction in regards to vein diameter, vein length, or relation of veins to joints. The choice of the location for intravenous cannulation, the use of tourniquets, the use of heating devices, and any techniques to palpate the vein will be left to the discretion of the Vascular Access Team member based on routine clinical practice. This study requires an unobstructed view of the subject's arm under standard hospital lighting conditions.

Investigators have up to 30 minutes or ONE attempt before the study allows for change of technique to the preference of the Vascular Access Team member.

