### **Follow-Up (for in-patients only)**

A member of the Vascular Access Team will see the patient in person three days after peripheral venous cannulation and each day thereafter according to routine practice. At the follow-up evaluation patency of the peripheral venous catheter and any complications associated with the peripheral venous catheter will be clinically assessed and documented. Follow-up will be completed once the patient has been discharged from the hospital or once the peripheral venous catheter placed as part of the study has been removed or replaced.

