### **Data Collection**

*The following variables will be assessed for all study patients at the time of peripheral venous cannulation:*

a) primary outcome measures:

- rate of successful initial placement of a peripheral venous catheter (investigators have up to 30 minutes or ONE attempt before the study allows for change of technique to the preference of the Vascular Access Team member)

b) secondary outcome measures:

- number of required needle sticks before successful placement of a peripheral venous catheter
- type of method that resulted in successful placement of a peripheral venous catheter
- number of visible veins suitable for cannulation (each continuous vein will be counted as one cannulation site)
- IV catheter gauge size utilized after completion of IV cannulation
- target vein location (bend of the elbow, forearm, back of hand, other) and side of extremity (right vs. left)
- use of warming of arm
- procedure time
- procedure associated complications
- Vascular Access Team member experience (years in practice)
- Vascular Access Team member survey:
  - subjective difficulty locating a suitable vein
  - subjective difficulty of venous access
  - subjective reasons for the difficulty of identifying veins
  - subjective impression of locating additional veins with VeinViewer device
  - subjective impression of usefulness of the VeinViewer device in successful placement of a peripheral venous catheter
- Patient survey:
  - usual number of IV attempts required
  - patients' satisfaction after completion of IV cannulation

c) clinical patient demographics will be derived from patient history and/or medical records:

- age
- gender
- height

- weight
- dominant hand
- date of procedure

*The following variables will be assessed for all in-patient study subjects, if available, at the time of follow-up:*

- catheter patency / need for replacement of catheter / type of catheter used for replacement
- presence of complications such as :
  - hematoma
  - phlebitis
  - thrombophlebitis
  - infiltration
  - nerve damage

All abstracted data, including a study number for each patient, will be stored on a password-protected research database on a hospital server at Lahey Hospital & Medical Center. Any identifier, except for date of procedure, will be removed after the follow-up has been completed.

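### Does the freedom to change technique after the first attempt undermine the by-arm comparison of the secondary outcomes?

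*Combined protocol and SAP*

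**What the plan says.** Study Objectives hypothesises that "the capability to successfully place lasting peripheral venous catheters is increased with the adjunct of the imaging technology", with fewer failed sticks. Secondary Objectives names complication rates and "durability of the catheter within each study treatment arm". Study Endpoints puts it differently: "Secondary endpoints include various measures of efficacy and quality of peripheral venous catheter placement as a factor of the method used". Data Analysis and Statistical Methods plans a direct comparison of the study groups for primary and secondary outcomes alike.

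Peripheral Venous Cannulation and Randomization of Study Groups sets a limit of 30 minutes, or "ONE attempt before the study allows for change of technique to the preference of the Vascular Access Team member". Data Collection repeats this limit beside the primary outcome. Its secondary outcomes include "number of required needle sticks before successful placement of a peripheral venous catheter", the "IV catheter gauge size utilized after completion of IV cannulation" and the "type of method that resulted in successful placement of a peripheral venous catheter". Follow-up covers in-patients only and ends at discharge or "once the peripheral venous catheter placed as part of the study has been removed or replaced".

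No section says how patients who changed technique enter the secondary analyses, and Limitations does not mention them.

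**The concern.** The secondary endpoints are described as showing the effect of the method, but after a failed first attempt the catheter may be placed by a method other than the assigned one. A control patient could receive imaging, and an imaging patient could be cannulated without it. The final gauge, the patency and the later needle sticks would still count for the original arm.

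This is realistic, because the devices are already in clinical use at the hospital and the choice is the operator's. The trial could then show better first-attempt success and yet report no difference in durability or gauge, partly because many controls ended up with imaging. A reader might take that as evidence that imaging does nothing for the life of the catheter.

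**Working it through.** **Inputs.** From Sample Size and Power Determination: first-attempt success 50% (control) and 70% (each imaging arm), two-sided 0.0167, 80% power, 125 per group, 400 enrolled. Allocation is 1:1:1. The documents give no rate of changing technique, no success rate for later sticks and no durability rates. Those are assumptions, shown over a range.

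**1. The plan's own figure.** With the pooled-variance formula, n = [2.393 × √(2 × 0.6 × 0.4) + 0.842 × √(0.5 × 0.5 + 0.7 × 0.3)]² / 0.20² = 124.2, rounded up to 125 per group; power at 125 is 80.3%. This concerns first-attempt success, which changes of technique do not touch.

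**2. Who may change after a failed attempt.** 400/3 = 133 per arm. Controls: 133.3 × 0.5 = 67. Each imaging arm: 133.3 × 0.3 = 40. Total 67 + 40 + 40 = 147. The 30-minute limit could add some patients who change before any stick.

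**3. Outcomes of the final catheter.** Let D be the difference between methods, and c and m the shares of control and imaging failures whose catheter is placed by the other kind of technique. If everyone is eventually cannulated and the failed stick itself does not affect durability, the by-arm difference is D × (1 − 0.5c − 0.3m).

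For illustration, assume 50% versus 70% patent by method and 133 per arm, tested at 0.0167. With c = m = 0.5, the control rate is 0.50 + 0.20 × 0.5 × 0.5 = 0.55 and the imaging rate is 0.70 − 0.20 × 0.3 × 0.5 = 0.67. The difference is 0.12, which is 60% of 0.20.

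| Share crossing | Kept, controls only | Kept, both directions | Power, controls only | Power, both directions |
|---|---|---|---|---|
| 0% | 100% | 100% | 83% | 83% |
| 25% | 87.5% | 80% | 71% | 61% |
| 50% | 75% | 60% | 56% | 35% |
| 100% | 50% | 20% | 25% | 4% |

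The 133 per arm is generous, since follow-up is limited to in-patients. At an assumed 80 per arm, power is already 59% with no crossing.

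**4. Needle sticks.** Mean sticks = 1 + (1 − p)/q, where p is first-stick success and q is success at each later stick.

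- No change (q equal to p): 1 + 0.5/0.5 = 2.00 versus 1 + 0.3/0.7 = 1.43, a difference of 0.57.
- All failures cross in both directions: 1 + 0.5/0.7 = 1.71 versus 1 + 0.3/0.5 = 1.60, a difference of 0.11.
- Imaging failures move to some third technique with q = 0.9 and controls stay at 0.5: 2.00 versus 1 + 0.3/0.9 = 1.33, a difference of 0.67, larger than with no change.

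Rank-test power is 92% with no change, 79% when half of the failures cross in both directions, and 59% when all do.

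**5. Which quantity the plan targets.** Study Endpoints describes the primary endpoint, too, in terms of the method used. Nobody would read that as anything but the assigned method. Reading the next sentence the same way agrees with Secondary Objectives, which names the treatment arm, and with the planned group comparison. On that reading the plan is consistent.

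**6. Would an added endpoint help?** One candidate counts a success only if the catheter was placed at the first attempt with the assigned technique and is still patent at day 3. With identical 60% patency in both arms it gives 0.5 × 0.6 = 30% versus 0.7 × 0.6 = 42%, with 36% power at 133 per arm to declare a difference although durability is the same. It largely repeats the primary endpoint. It would also count as failures catheters taken out before day 3 because they were no longer needed, as the listed data do not separate reasons for removal.

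**The case for a change.** The strongest case for a change is that dilution is material at the plan's own rates, that clarification is cheap, and that silence invites two errors: taking a diluted null for proof of no method effect, or analysing by the technique actually used and losing the protection of randomisation. The arithmetic behind this is sound. In the two-way crossover model every switching scenario shrinks the difference, including in a check with varying patient difficulty. Small by-arm differences in durability or gauge should therefore be read with care.

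The claim that the direction is known goes too far. The rule allows any technique the operator prefers, not only the other study method, and the third-technique example widens the needle-stick gap. Moving between the two imaging arms dilutes nothing in an imaging-versus-control comparison under this model. Durability is diluted only if method affects it, and no durability effect is quantified. The plan neither powers the secondary outcomes nor assigns 0.0167 to them.

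The remark in Limitations that long-term outcomes should not depend on method defends the length of follow-up against late complications. It does not clearly concern patency in hospital, so it is weak evidence that a null result would be misread.

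**Conclusion.** No change to the plan is needed. The secondary comparisons by randomised arm are valid estimates of the effect of starting with a given method, which is also the decision a vascular access team faces. They may understate the difference between methods as such: the by-arm durability difference lies between 20% and 100% of it under two-way crossover, and the needle-stick difference between 0.11 and 0.57 under the rates assumed above. Where the trial falls in those ranges depends on a rate of changing technique that the documents do not give; with no crossing there is no loss.

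The available remedies would not improve the analysis. Rewording the endpoint leaves the same comparison in place. Tabulating the successful method by arm is in effect already planned. A first-attempt-and-patent composite would mostly restate the primary result. Analysts can fill the gap by reporting secondary results as effects of the assigned first-attempt strategy beside the successful method in each arm, and by treating any analysis by technique actually used as exploratory.

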### **Sample Size and Power Determination**

The study was designed such that we will need to enroll at least 125 patients per group (375 patients total for all three groups) to have 80% power if the estimated percentage with success in the control group is 50% and 70% in either of the study groups using a two-sided  $p < 0.0167$  for determining significance (study alpha was divide equally between the three groups).

We have therefore chosen to include 400 patients in the study. We anticipate that this initial data set will provide useful information regarding the effectiveness of the device in difficult access situations. In addition, it will give information about variability of data between patients that will guide the design of any future device and further studies that will answer more specific clinical questions.

Due to the need for appropriately trained staff to be available, the study will only be offered during hours when one of the trained Vascular Access Team members / co-investigators is available. During this time frame, the Vascular Access Team typically encounters approximately 50 patients per week. We anticipate that approximately 40% of these patients will meet study inclusion criteria. We estimate an approximate 60% study recruitment rate. We therefore expect that approximately 12 patients will be recruited into the study per week. The study is therefore estimated to be complete within 8 months.

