### **Data Analysis and Statistical Methods**

Direct study group comparison of the primary and secondary outcome variables will be performed using routine statistical tests utilizing a statistician at Tufts CTSI. In addition, the study will collect limited descriptive information pertinent to the effectiveness of visualizing superficial peripheral veins.

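### Testing the three primary comparisons step-down instead of all at a fixed 0.0167 would add power at no extra enrolment (an improvement, not an error)

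*Combined protocol and SAP*

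**What the plan says.** All references are to the combined protocol and SAP.

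- **Sample Size and Power Determination** sets one two-sided threshold of 0.0167 and gives the reason: "study alpha was divide equally between the three groups". The requirement is 125 per group (375 in total) for 80% power, where "the estimated percentage with success in the control group is 50% and 70% in either of the study groups". Planned enrolment is 400.
- **Data Analysis and Statistical Methods** adds only this: "Direct study group comparison of the primary and secondary outcome variables will be performed using routine statistical tests". It names no test, no order of testing and no multiplicity procedure.
- **Study Objectives** frames the trial as conventional placement "compared to two established methods utilizing NIR vein imaging".
- **Peripheral Venous Cannulation and Randomization of Study Groups** gives simple randomization in a 1:1:1 ratio.

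The overall alpha of 0.05 is not printed and the three comparisons are not listed. Both are inferred: 0.05/3 = 0.01667, and three arms give three pairwise contrasts.

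**The concern.** A flat split tests every comparison as if all three nulls could still be true, even after one has been rejected. With three arms that is needlessly strict: two true equalities imply the third, so if one is false at most one of the others can be true. After the first rejection, the fixed rule leaves part of the allowed error unspent.

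The loss falls mainly on the second conclusion. If both NIR methods work, that conclusion is that both beat conventional placement. If only one works, it is that this arm beats control, because the first rejection may have been NIR against NIR. No conclusion under the current rule would be invalid. What is at stake is power that the trial could have from the same patients.

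**Working it through.** **Inputs.** Control 50%, NIR 70%, two-sided 0.0167, 80% power, 125 per group and 400 in total come from the sample-size section; 400/3 is about 133 per group. The scenarios 50/50/70 (one NIR arm works) and 50/60/70 are my assumptions.

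**Step 1: reproduce the plan's figure.** The pooled-variance formula without continuity correction is

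n = [z(1−α/2)·√(2p̄(1−p̄)) + z(power)·√(p₁(1−p₁)+p₂(1−p₂))]² / (p₂−p₁)²

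Here z(1−α/2) = 2.393, z(power) = 0.842, p̄ = 0.60, 2p̄(1−p̄) = 0.48 and p₁(1−p₁)+p₂(1−p₂) = 0.25 + 0.21 = 0.46. Then n = (2.393×0.6928 + 0.842×0.6782)² / 0.04 = 124.2, so 125 per group. The stated figure is correct, and it corresponds to an uncorrected chi-square (pooled z) test.

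**Step 2: the two rules.**
- Fixed: reject any of the three comparisons with p ≤ 0.05/3.
- Step-down (Shaffer's refinement of Holm): test the smallest p-value against 0.05/3; if it is significant, test each of the other two against 0.05.

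The first step is identical, so if all three nulls are true the error is identical: 0.0500 at 125 and 0.0439 at 133 when all rates are 50%. If exactly one null is true, it is tested at no more than 0.05. Step-down rejects everything that the fixed 0.05/3 rule rejects.

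**Step 3: power and error.** Exact enumeration of all three-arm outcomes, pooled z-test, equal arms, fixed to step-down:

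| Scenario and quantity | 125 per group | 133 per group |
|---|---|---|
| 50/70/70, each NIR arm vs control | 0.806 to 0.865 | 0.828 to 0.892 |
| 50/70/70, both NIR arms superior | 0.699 to 0.816 | 0.725 to 0.853 |
| 50/70/70, at least one NIR arm superior | 0.914, unchanged | 0.931, unchanged |
| 50/50/70, working arm vs control | 0.806 to 0.869 | 0.828 to 0.889 |
| 50/50/70, true null rejected (error) | 0.019 to 0.049 | 0.017 to 0.057 |
| 50/60/70, 70% arm vs control | 0.806 to 0.819 | 0.828 to 0.840 |
| 50/60/70, 60% arm vs control | 0.222 to 0.340 | 0.222 to 0.379 |

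Check on the third row at 125: 2×0.8064 − 0.6986 = 0.914 (fixed) and 2×0.8650 − 0.8158 = 0.914 (step-down).

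**Step 4: the gain in patients.** Under the fixed split, power for both NIR arms is 0.813 at 153 per group and 0.819 at 154. Matching the 0.816 that step-down gives at 125 therefore takes 154 per group: 3×154 = 462 against 375. Matching 0.865 per comparison takes 144 per group.

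**Step 5: choice of test.** With Fisher's exact test the one-true-null error at 50/50/70 rises only from 0.014 to 0.036 at 125 and from 0.012 to 0.043 at 133. Power for both NIR arms goes from 0.648 to 0.776 and from 0.680 to 0.819. First-step power per comparison is then 0.769 and 0.796.

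**The case against.** The strongest reply is that nothing is broken: Bonferroni is legitimate, the 80% target is met, and a team may prefer the simpler rule. That stands, and it is why this is put as an improvement.

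Four narrower points also carry weight.

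- **The largest gain is for a claim with no stated power target.** The plan powers each NIR arm against control, not both together. On that measure the gain is about six points, and only about one point for the 70% arm at 50/60/70.
- **More rejections also means more false ones.** With one ineffective NIR arm, the chance of a false claim rises roughly threefold at 133 per group, to 0.057. That excess over 0.05 comes from binomial discreteness with exactly equal arms. Averaged over 60 simulated 400-patient allocations under simple randomization, the error was 0.050 (range 0.046 to 0.055).
- **The family of three is inferred.** If only the two control comparisons matter, Holm on those two (0.025, then 0.05) gives 0.881 per comparison and 0.825 for both at 50/70/70 with 125 per group, better than the three-comparison rule. At 50/50/70 it gives 0.844 for the working arm, against 0.869. It offers no protected NIR-against-NIR test.
- **Intervals no longer match the tests simply.** This matters because the endpoints section speaks of estimation.

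These bear on which step-down rule and which test to adopt. None gives the fixed split a power advantage for the same three comparisons.

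**Conclusion.** The point holds as a low-cost improvement. For the primary endpoint, the fixed split gives up about six points of power per NIR-against-control comparison when both NIR arms reach 70%, or when only one does. It gives up 12 to 13 points for showing both superior. It costs nothing in the chance of at least one NIR success at 50/70/70, and step-down does not rescue a 60% arm.

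This rests on an overall alpha of 0.05, three pairwise comparisons, equal arms and the uncorrected chi-square. The threshold is established only for the primary endpoint; the plan does not say whether it also governs the secondary outcomes. Leaving the plan unchanged invalidates no conclusion.

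**What to change.** Before outcome data are examined, add to Data Analysis and Statistical Methods:

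*The three pairwise comparisons of the primary endpoint are tested step-down (Shaffer-Holm) with [named two-sample test]: the smallest p-value against 0.05/3; if significant, the other two each against 0.05.*

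- **Test.** The uncorrected chi-square agrees with the sample size. Fisher's exact keeps actual error below 0.05 in the cases computed, with first-step power of 0.77 at 125 and 0.80 at 133 per group.
- **Sample size.** Keep 125 per group and 80% as the conservative first-step figure.
- **Intervals.** Report 98.33% intervals for the differences (1 − 0.05/3) and state that they may include zero when a second-step test is significant.
- **Alternative.** If NIR against NIR is not to be a protected claim, say so and use Holm on the two control comparisons.

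The cost is one sentence plus the interval caveat, and no patients. Timing needs care: under Study Monitoring the principal investigator reviews collected data every four weeks from first enrolment, so the amendment should be dated and should record what had been seen by then.
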